1.4 DESIGN FEATURES

Only newly diagnosed cases of sarcoidosis with tissue confirmation of granuloma and a clinical course compatible with sarcoidosis, that is, a systemic granulomatosis of unknown etiology are eligible for the study. Newly diagnosed cases are of interest for accuracy and consistency of recall. A newly diagnosed case is defined as a patient who had tissue confirmation less than six months prior to entry into the study. Initially, cases are recruited at each participating Clinical Center, without regard to type of clinical disease (i.e., erythema nodosum or Löfgren's Syndrome; acute or chronic sarcoidosis, excluding patients with fibrotic lung disease; fibrotic lung disease; or extrapulmonary sarcoidosis). Clinical Coordinating Center staff review the distribution of enrolled cases periodically to ensure that appropriate proportions of cases in each of the defined categories of disease are enrolled.

Population-based controls are selected through random digit dialing. Controls are matched to cases on age (within five years), gender and self-designated race (black, white, other). Random digit dialing facilitates the selection of a control group that approximates a probability sample in the population.

Only individuals 18 years of age or older are eligible. Cases or controls cannot have active tuberculosis or be taking anti-tuberculosis therapy or have a history of chronic beryllium disease. Potential controls with a past history of sarcoidosis, granulomatous hepatitis, primary biliary cirrhosis, Bell's palsy, undiagnosed uveitis, Crohn's disease and erythema nodosum of unknown etiology are excluded from the study. Cases and controls must be competent to sign consent forms for study participation and must be willing to participate in all required study evaluations.

Both cases and controls complete an entry evaluation for the collection of required data and biological specimens for future evaluation. The entry evaluation includes collection of demographic

information (age, gender, race, residence, marital status, etc.), medical history, environmental, and occupational exposure history, questions about the individual's family (first degree relatives), standardized psychosocial data on health related quality of life, and medical care usage.

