3.3 INFECTIOUS, OCCUPATIONAL AND ENVIRONMENTAL FACTORS

An interviewer-administered occupational / environmental questionnaire is used to obtain information to address the following hypotheses:

- Sarcoidosis patients (cases) are more likely to report employment in particular occupations or occupational categories when compared with a non-sarcoidosis referent group (controls). The categories considered include:
 - A. Employment in metal dust and metal fume associated industries.
 - B. Employment as health care workers.
 - C. Employment as child care providers and educators.
 - D. Employment as firefighters.
 - E. Employment in the military.
 - F. Employment in agriculture.
 - G. Occupational exposure to organic dusts.
 - H. Employment in mechanically ventilated buildings.
 - I. Employment in environments where exposure to microbial bioaerosols occurs.
 - J. Occupational exposure to chemicals that can produce hypersensitivity pneumonitis or granulomatous lung disease (e.g., isocyanates, pyrethrums).
 - K. Employment indoors.
 - L. Employment in dusty trades.

- M. Frequent close contact with co-workers or others during the work day.
- 2. Sarcoidosis patients (cases) are more likely to report particular environmental exposures when compared with a non-sarcoidosis referent group (controls). The exposures considered include:
 - A. Avocational exposure to metal dust and fumes (e.g., welding, jewelry making).
 - B. Avocational exposure to children.
 - C. Exposure to microbial contamination and bioaerosols in the home environment.
 - D. Exposure to organic dusts in a home environment.
 - E. Tobacco exposure.
 - F. Prior use of medications known to produce hypersensitivity lung diseases or granulomatous disease in other organs.
 - G. Rural residence.
 - H. Exposure to animal (including bird) antigens.

As part of the occupational and environmental questionnaire, antecedent occupational histories are recorded. Case and control occupations and industries are coded using standardized industrial codes (SIC) and standardized occupational codes (SOC) to test the following hypotheses:

 Sarcoidosis patients (cases) are more likely to have been employed in certain occupational categories or industries when compared with a non-sarcoidosis referent group (controls).

Specifically, we propose to test the hypothesis that occupational categories sharing common chemical or biological material exposures confer similar risks of sarcoidosis.

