Multiorgan disease is defined as tissue confirmation in at least one organ, and either clinical or pathological involvement in another organ(s), as outlined in Table 6-1. The record of organ involvement for cases is based on abnormalities ever observed in the set of definitions in use November 1996 - March 1998, and in the revised definitions in use starting April 1998. The revisions made to the criteria for organ involvement in April 1998 were clarifications of wording, deletion of evidence of treatment response as a criterion (because almost none of the ACCESS cases have had a definitive course of treatment at the time of study entry and some of these abnormalities may respond to the same treatment if used for other diseases), and regrouping of the categories into those that are common, those that are unusual but serious, and other organ involvement.

Individuals with chronic beryllium disease are excluded from the study. Potential cases with occupational histories indicating possible beryllium exposure are excluded from the study unless both blood and bronchoalveolar lavage proliferation studies indicate a negative response to beryllium. Fungal lung disease and tuberculosis should be ruled out. Specifically, all cases should have acidfast bacillus (AFB) and fungal cultures of all available tissue performed and appropriately stained unless the diagnosis was confirmed by the Kveim agent. In potential cases undergoing bronchoscopy, bronchial washings should always be obtained specifically for fungal and AFB cultures. Potential cases who live in areas where histoplasmosis is endemic or who have risk factors for tuberculosis should have appropriate tests performed on tissue specimens (cultures of biopsy specimens required) to exclude tuberculosis and fungal infections (especially histoplasmosis). In particular, adequate samples should be cultured, if possible. At a minimum, slides of tissue should be stained for mycobacteria and fungi. Fungal serology and measures of H. capsulatum antigen are not expected to contribute to the diagnosis and are not used in ascertaining case eligibility. All slides for cases enrolled after September 1997 are reviewed under polarized light to determine whether birefringent material is present. A review for birefringent material on the slides of cases enrolled prior to September 1997 is performed if the slides are available.

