6.2 CASE SELECTION

It is planned that the total study population will consist of 720 cases and 720 controls. Each Clinical Center enrolls, interviews, examines and collects blood specimens from 72 cases with sarcoidosis and enrolls, interviews and collects blood specimens from 72 matched controls during the recruitment period (November 1, 1996 through June 30, 1999).

Cases may be recruited from a variety of clinical settings, including inpatient, hospital-based outpatient, and non hospital-based outpatient. Each Principal Investigator defines, in advance, the geographic area from which the center recruits patients for the study. Permission to contact patients identified in a clinical setting must be obtained initially from the attending physician of record, in advance of study enrollment. Potential cases are informed that a payment will be given to reimburse them for parking costs, meals and other expenses (including lost time from work) at the medical center, and transportation costs.

At the time of enrollment into the study, patients are categorized according to their clinical condition at the time of initial diagnosis, i.e., the day of biopsy confirmation. Table 6-2A outlines the disease categories that were used to describe cases beginning November 1996. An additional revised classification system was used beginning September 1997 and is given in Table 6-2B. The purpose of revising the disease categories is to encourage use of information on facets of the clinical presentation of sarcoidosis that were not readily appreciated in the hierarchical, initial classification of disease categories. This information is used in ACCESS to assess the spectrum of clinical sarcoidosis presentations represented among the ACCESS cases.

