6.4 INCLUSION/EXCLUSION CRITERIA AND CONFIRMATION OF ELIGIBILITY

Only patients 18 years of age or older may be enrolled in the study. Patients cannot have active tuberculosis or be taking anti-tuberculosis therapy. Potential controls with a past history of sarcoidosis, chronic beryllium disease, fungal diseases treated with systemic chemotherapy, granulomatous hepatitis, primary biliary cirrhosis, Bell's palsy, uveitis, Crohn's disease, and erythema nodosum of unknown etiology are excluded from the study.

Potential cases and controls must be competent to sign consent forms for study participation and must be willing to participate for the length of the study. They may be excluded from the study if there is evidence that they may not comply with all study requirements. Potential cases and controls must be able to respond directly to questions on the study forms to be eligible for inclusion in the study. The eligibility of potential cases and controls is determined by the Clinical Center Coordinator through a combination of record review and telephone and personal interview. The Coordinator explains the nature of ACCESS to the potential cases and controls. If the potential case or control is interested in participating in ACCESS, the Coordinator administers a brief structured questionnaire addressing eligibility issues not gleaned from the medical record or telephone interview.

Potential cases and controls who are eligible and agree to enrollment, are asked to sign one or more consent forms to participate, depending upon the individual's case/control status (see Chapter 7). Cases and controls are identified only by a patient name code and identification number. The patient's name code and identification number serve to conceal the personal identity from the ACCESS Clinical Coordinating Center and Clinical Center staff and to maintain confidentiality. The patient's name code and identification number are recorded on separate ACCESS logs for cases and controls. These logs include the following information:

- 1. Date of initial contact.
- 2. Age.
- 3. Gender.
- 4. Race.
- 5. Health care coverage.

The reasons for ineligibility are recorded for all cases and controls deemed ineligible to participate in ACCESS. As noted in Section 6.2 completion of screening logs for cases was discontinued in October 1997.

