7.2 ORIENTATION OF CONTROLS

Controls are informed of the nature of the study and the method by which they were invited to participate. Potential controls are informed that random digit dialing methods are used to identify individuals with age, gender, and race matching those of a particular patient with sarcoidosis within the same telephone exchange.

Controls are informed that their participation in the study involves an interview with completion of a questionnaire and collection of a blood sample. There are no other procedures, and no follow-up is planned. Controls are informed that they will be reimbursed for their expenses to participate in the study. The amount varies among Clinical Centers and depends upon whether or not the individual has to make a special trip to the Clinical Center. Each individual receives a minimum of \$25 for ACCESS-related expenses.

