10.1 OVERVIEW

The purpose of this chapter is to provide guidelines for the collection and disposition of biological specimens (blood and bronchoalveolar lavage cells and fluid) in ACCESS. Bronchoalveolar lavage (BAL) specimens are collected as residual specimens from clinically indicated bronchoscopy procedures.

A summary of blood samples required from cases and controls in ACCESS follows:

Whole blood:	54 ml	in EDTA	
	40 ml	in heparin	only for those Clinical Centers providing cell
			pellets for RNA analysis by differential display
			polymerase chain reaction (DD-PCR) as part of
			the special laboratory study at the Beth Israel
			Deaconess Medical Center; unless specifically
			notified by the Executive Committee ACCESS
			Clinical Centers other than the Beth Israel
			Deaconess Medical Center do not collect these
			specimens.

Study forms and data files are used to track processing, shipment and receipt of biological specimens used in ACCESS from Clinical Centers to Core Laboratories, Special Study Laboratories and the Central Repository (see Chapter 6 of ACCESS Procedures Manual, Volume I for details). All specimens collected and shipped including (blood and bronchoalveolar lavage) must be handled according to universal precautions including double-bagging of mailed specimens. If a specimen is known to be infectious, it must be shipped following the additional procedures outlined in the ACCESS Procedures Manual Volume I, Chapter 6.

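### The case-only rule on possible beryllium exposure can lower the odds ratio for occupational metal exposure, by an amount the protocol does not give and that may be small

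*Protocol*

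**What the plan says.** **Cases.** Section 6.1: "Potential cases with occupational histories indicating possible beryllium exposure are excluded from the study unless both blood and bronchoalveolar lavage proliferation studies" show no response to beryllium. The trigger is an exposure history, and two negative tests lift the exclusion.

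**Controls.** Section 6.4: "Potential controls with a past history of sarcoidosis, chronic beryllium disease, fungal diseases treated with systemic chemotherapy" and several other conditions are excluded. The beryllium item is a disease. Neither section 6.3 nor 6.4 gives controls an exposure criterion. Section 7.2, after listing the interview and blood sample, adds: "There are no other procedures, and no follow-up is planned".

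**Overview.** Section 1.4 gives one disease-based criterion for both groups: neither may "be taking anti-tuberculosis therapy or have a history of chronic beryllium disease". It does not mention the exposure rule.

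**Source of lavage.** Section 10.1 says of bronchoalveolar lavage that "specimens are collected as residual specimens from clinically indicated bronchoscopy procedures", and Table 8-1 requires the lavage form only where such data exist. Section 6.1 also admits cases on skin or mediastinal node biopsy and, in Löfgren's syndrome, on a Kveim test.

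**Hypotheses.** The first occupational category in section 3.3 is "Employment in metal dust and metal fume associated industries". Item L of that list covers dusty trades, and a later hypothesis concerns risk by duration of employment.

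**Analysis.** Section 12.3.2 relies on matched-pair methods and conditional logistic regression. Chapter 12 contains no restriction or sensitivity analysis for the beryllium rule.

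**The concern.** A case-control odds ratio is valid only if exposure does not influence selection differently in the two groups. Here an occupational exposure can keep a potential case out, but the same exposure never keeps a control out. Jobs with possible beryllium exposure plausibly overlap the metal dust and fume industries that section 3.3 sets out to study.

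Excluding patients who have beryllium disease is not a bias, because the study defines its cases by unknown etiology. The difficulty is with exposed patients whose disease really is sarcoidosis. They are lost if they never had lavage, because the exception requires both tests, or if a test is falsely positive. The odds ratio for occupational metal exposure is then understated, and a weak or null result would be hard to read. Dusty trades and the duration analysis are affected in part, as far as they involve the same jobs.

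**Working it through.** **Inputs from the protocol**
- Size (section 6.2): "It is planned that the total study population will consist of 720 cases and 720 controls", matched 1:1.
- Two-sided alpha 0.05, so Z = 1.96 (section 12.2.1).
- Reference scenario: odds ratio 2.0, control exposure p0 = 0.05, power at least 90% (section 12.2.1). Table 2 gives 0.909 at correlation 0.

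**Assumed input**
- f, the share of metal-exposed true sarcoidosis cases removed by the rule. The protocol gives no value.

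**Step 1: reproduce the protocol's figure.** For 1:1 matching the formula in section 12.2.1 reduces to

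power = Φ(δN / √(ψN) − 1.96), with δ = p1 − p0, ψ = p1 + p0 − 2·p1·p0 − 2·cov, and p1 = OR·p0 / (1 − p0 + OR·p0).

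At OR 2.0, p0 = 0.05 and cov = 0:
- p1 = 0.10/1.05 = 0.0952
- δ = 0.0452
- ψ = 0.0952 + 0.05 − 0.0095 = 0.1357
- δ·√(N/ψ) = 3.295
- power = Φ(3.295 − 1.96) = Φ(1.335) = 0.909, as in Table 2.

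**Step 2: effect of the rule on the odds ratio.** The matched odds ratio is the number of pairs with only the case exposed divided by the number with only the control exposed. Removing a share f of exposed true cases multiplies the first count by (1 − f) and leaves the second unchanged:

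observed OR = true OR × (1 − f).

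The factor does not depend on exposure prevalence and acts within every age, gender and race stratum, so matching does not remove it. Conditional logistic regression cannot recover people who were never enrolled. A simulation of 4 million matched pairs checked this, with control exposure of 5% in half of the pairs and 15% in the other half, true OR 2.0 and f = 0.20. It gave 1.60, which is 2.0 × 0.80.

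**Step 3: size for assumed f.** Enrolment still runs to 720 pairs, so the power for the shifted odds ratio can be read from the protocol's own tables (control exposure 0.05):

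| Assumed f | Observed OR | Power, correlation 0 (Table 2) | Power, correlation 0.5 (Table 1) |
|---|---|---|---|
| 0 | 2.00 | 0.909 | 0.995 |
| 0.05 | 1.90 | 0.856 | 0.987 |
| 0.10 | 1.80 | 0.783 | 0.967 |
| 0.20 | 1.60 | 0.573 | 0.849 |

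In the reference scenario about 720 × 0.0952 = 68.6 cases are exposed, so f = 0.10 corresponds to about 7 people.

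**Step 4: what f consists of.** f is the share of metal-exposed true cases with a possible beryllium history, times the share of those not cleared by both tests. Assuming 10% × 50% gives f = 0.05 and moves 2.0 to 1.90. Assuming 25% × 50% gives f = 0.125 and moves it to 1.75.

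**Step 5: the same restriction in both groups.** Repeating the simulation with the same share of exposed people removed from cases and controls returned an odds ratio of 2.00.

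**The case against.** The rule has a sound purpose. Section 2.2 treats chronic beryllium disease as indistinguishable from sarcoidosis apart from its known agent. Admitting exposed patients who have not been cleared could let beryllium disease in as sarcoidosis and push the metal odds ratio upward. This stands: only the loss of true sarcoidosis cases counts as bias.

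Loss through missing lavage may be uncommon. Section 7.1 calls bronchoscopy a frequently used diagnostic procedure with lavage a routine part of it, section 2.1 puts lung involvement at 90%, and Kveim confirmation is confined to Löfgren's syndrome. Section 10.1 describes how specimens reach the study and does not say that an exposed patient could not be tested. This also stands and keeps f uncertain. But no passage makes lavage or beryllium testing part of the required evaluation, so f cannot be taken as zero.

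A reader might also infer four stronger things that the documents do not support:
- **All metal-exposed cases are removed.** The rule reaches only occupational histories of possible beryllium exposure, and only where both tests are not negative.
- **A real association would be cancelled or reversed.** Reducing a true 2.0 to 1.0 needs f = 0.5, and nothing in the protocol points to a value that high.
- **The HLA-by-metal interaction in section 3.6.1 is biased.** If loss through missing lavage is independent of genotype, (1 − f) multiplies the metal odds ratio equally in each HLA group and cancels in their ratio.
- **The avocational metal hypothesis is biased.** The trigger is occupational, so that analysis is touched only where the person also has such a job history.

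Finally, metal work is one of 13 occupational and 8 environmental categories in section 3.3, section 3.7 describes the study as hypothesis-generating, and a restricted analysis could sit in an analysis plan not shown here. This bears on priority. It does not remove the asymmetry, which the eligibility criteria themselves create.

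**Conclusion.** The concern holds in a limited form. Sections 1.4, 6.1 and 6.4 together apply an exposure-based exclusion to cases and only a disease-based one to controls, and Chapter 12 does nothing to offset it. The odds ratio for occupational metal dust and fume exposure is the true value times (1 − f), so the effect is downward or nil. It is nil only if every exposed true sarcoidosis case had both tests and both were negative.

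The size is unknown. The values for f of 0.05 to 0.20 are illustrations, and f may be below them. They assume that unexposed cases and all controls are otherwise selected without regard to exposure. This is a cheap improvement to the metal and dust analyses. It is not a defect that must be fixed before the study can be used, and comparisons outside metal and dust are not shown to be affected.

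**What to change.** Add to section 12.3.2, for the occupational metal and dust analyses, including the analysis by duration of employment:

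1. Code possible beryllium exposure from the industry and occupation (SIC/SOC) histories already collected, by one written rule applied blind to case or control status.
2. Drop every pair in which either member meets the rule, and state that the odds ratio refers to people without possible beryllium exposure.
3. Report the unrestricted analysis as secondary, noting that any bias from the case-only exclusion is downward.

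The beryllium criteria in sections 1.4, 6.1 and 6.4 should also be reconciled. This point takes no position on which eligibility rule is right.

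The cost is one derived variable and a paragraph of analysis text. Some pairs are lost, and the conclusion about metals becomes narrower. Some bias remains if the coded rule is narrower than the judgement of possible exposure made at enrolment.

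A count of potential cases turned away would help to size f but is not part of the fix. Case screening logs stopped in October 1997 while recruitment ran to June 1999, and section 6.2 says no questionnaire data are taken from ineligible cases.
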